3.1.10. Medical History

A medical history of the subject will be taken during the screening period. The onset and resolution date or ongoing will be recorded for each condition reported. If no part (including year) of the onset or resolution date is known, then the condition will be reported as occurring less than 5 years ago or more than or equal to 5 years ago.

Medical history will also include a report of tobacco and alcohol use. For each item subjects are to report whether they never used, are currently using, or have formerly used. If subjects are a current or former user, they are to indicate the number of years they used the product, and former users are to indicate the stop date of using the product.

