3.4.4. EFP Risk Factors and EFP History

EFP risk factors and EFP history characteristics will be summarized by assigned region (buttock or thigh) and overall for both the safety population and effectiveness population, and will include:

- Family history of cellulite
- Medical history of Dupuytren's disease, knuckle pads, Ledderhose's disease, diabetes, epilepsy (see [section 3.2.6.4](#))
- Age at EFP symptom onset (in years)
- Prior treatments for EFP including Liposuction, Laser, Massage, Radiofrequency, Drug, Mesotherapy, Cream, Other or None. Subjects can report more than one prior EFP treatment.
- Number of prior EFP treatments (0, 1, 2, or ≥ 3)
- Time since most recent EFP treatment (in years)

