3.5.3. Imputation of Partial Dates

Study visit dates, birthdates, informed consent date, injection dates/times, all assessment dates, all lab dates, and date of completion/last contact date must be complete dates; no imputations will be done. No imputations will be done for partial medical history onset/resolution dates (except EFP onset date), partial alcohol/tobacco stop dates, partial AEs onset/end dates and partial concomitant medication start/stop dates. All AEs with a missing onset day will be considered treatment emergent except if the onset month/year is prior to the first injection date. All medications with a missing onset and stop day will be considered concomitant except if the stop month/year is prior to the first injection date.

For EFP onset date and prior EFP medications/treatment dates, missing EFP onset dates or missing prior EFP medication/treatment start dates will be imputed with the 1st day of the month and missing onset month will be imputed with January. If the EFP onset date is indicated as completely unknown but starting less than 5 years ago, the EFP onset date will be imputed as the informed consent date minus 5 years. If the EFP onset date is indicated as completely unknown but starting more than 5 years ago, the EFP onset date will not be imputed. Missing EFP medication/ treatment end days will be imputed with the last day of the month and missing end

months will be imputed with December, except if the end year is equal to the date of injection year and then the EFP medication/treatment end date will be imputed with the first injection date.

All the missing date imputation will be used for the summary tables only; no imputation will be applied for the subject listings.

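### An undatable EFP onset recorded as under 5 years ago is imputed at exactly 5 years, outside its own category, so age at onset is biased low; undatable older onsets are left missing with no count required

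*SAP*

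**What the plan says.** SAP 3.1.10 (Medical History) covers a condition for which not even the year is known: "then the condition will be reported as occurring less than 5 years ago or more than or equal to 5 years ago". SAP 3.2.6.4 and Table 7 take the EFP onset date from the medical history data, and SAP 3.5.3 uses the same 5-year split for it.

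SAP 3.5.3 then gives three rules for EFP onset:

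- **Partly known date:** it "will be imputed with the 1st day of the month and missing onset month will be imputed with January".
- **Wholly unknown, recent:** "If the EFP onset date is indicated as completely unknown but starting less than 5 years ago", then "the EFP onset date will be imputed as the informed consent date minus 5 years".
- **Wholly unknown, older:** "If the EFP onset date is indicated as completely unknown but starting more than 5 years ago, the EFP onset date will not be imputed".

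Table 7 derives age at onset as onset date minus date of birth, divided by 365.25 and truncated to a whole number, and refers to 3.5.3 for unknown dates. SAP 3.4.4 summarizes it by region and overall, in both the safety and the effectiveness population. Imputed dates feed the summary tables only; listings show the data as recorded.

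**The concern.** The recent-onset rule assigns a date that the subject's own answer excludes. Her answer says fewer than 5 years; the table will treat her as having had EFP for exactly 5. That is the earliest limit of the interval, so the error runs in one direction for everyone in the group.

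The older-onset rule assigns nothing, so Table 7 cannot produce an age for those women. Among subjects who cannot date their onset, the summary therefore keeps every recent case and omits every long-standing one. Whether a woman contributes depends on disease duration, and nothing in the SAP requires the number omitted to be shown.

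At stake is how accurately one disease-history characteristic describes the enrolled population.

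**Working it through.** The plan gives no figure to reproduce.

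**Inputs from the documents**

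- Categories for an undatable onset: under 5 years, or 5 years and more (SAP 3.1.10).
- Imputed onset for the first category: consent date minus 5 years (SAP 3.5.3).
- Age at onset: (onset date − date of birth)/365.25, truncated (SAP Table 7).

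**Inputs not in the documents (assumptions, shown as ranges)**

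- T: true years from onset to consent in the recent group, 0 ≤ T < 5.
- f: share of subjects contributing an age whose date comes from the 5-year rule.
- q: share of subjects with no age because onset is undatable and older.
- D: mean onset age of those missing minus mean onset age of those observed.

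**Step 1. Is the imputed value inside its category?** Consent minus 5 calendar years is exactly 5 years ago. It fails the under-5 condition and meets the 5-or-more condition. The partial-date rule behaves differently: the 1st of a known month, or January of a known year, stays inside what the subject reported.

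**Step 2. Error per subject in the recent group.** With A the age at consent, imputed age at onset is A − 5 and true age at onset is A − T.

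Error = (A − 5) − (A − T) = T − 5, which is at least −5 and below 0.

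| Assumed T | Mean error under the SAP rule |
|---|---|
| Uniform on 0–5 | 2.5 − 5 = −2.5 years |
| Uniform on 0–1 | 0.5 − 5 = −4.5 years |
| Uniform on 4–5 | 4.5 − 5 = −0.5 year |

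Truncation to whole years leaves these means essentially unchanged. About 10% of affected subjects (T uniform on 0–5) to 50% (T on 4–5) still get the correct whole-year age.

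**Step 3. Effect on the reported mean.** Shift = f × mean(T − 5).

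| f | T uniform on 0–5 | Limit (T near 0) |
|---|---|---|
| 5% | 0.05 × −2.5 = −0.125 year | 0.05 × −5 = −0.25 year |
| 20% | 0.20 × −2.5 = −0.5 year | 0.20 × −5 = −1.0 year |

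**Step 4. The older group.** The mean over all subjects is the observed mean plus q × D, so the bias of the observed mean is −q × D. At q = 20%:

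- D = −5 gives +1.0 year.
- D = 0 gives no bias.
- D = +5 gives −1.0 year.

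Nothing in the documents fixes the sign of D.

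**Step 5. Would the interval midpoint do better?** With consent minus 2.5 years the error is T − 2.5.

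| Assumed T | Mean absolute error, SAP rule | Mean absolute error, midpoint |
|---|---|---|
| Uniform on 0–5 | 2.5 years | 1.25 years |
| Uniform on 4–5 | 0.5 year | 2.0 years |

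The midpoint is better if T is spread over the interval and worse if T clusters near 5.

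**Step 6. Category wording.** SAP 3.1.10 has the older group "reported as occurring less than 5 years ago or more than or equal to 5 years ago", so it includes exactly 5 years. SAP 3.5.3 has "completely unknown but starting more than 5 years ago, the EFP onset date will not be imputed", which does not. Exactly 5 years therefore has no rule in 3.5.3, yet it is the value that 3.5.3 imputes.

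**The case against.** The best defence has four parts.

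1. **The boundary is a technicality.** No planned analysis sorts the imputed date back into the two categories, and one day later would be inside the interval with practically the same age. This is right about the category label. It does not remove the bias: a value at the earliest limit is too low by T − 5 whichever side of the line it falls.

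2. **The rule follows the SAP's convention of using the earliest possible date.** This is partly right. For partial dates the convention costs at most a month or a year and stays inside the known interval. Here it costs up to 5 years and leaves the interval.

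3. **Leaving the older group missing is defensible.** This stands. The interval has no lower bound, so any imputed date would be invented. The women remain in both analysis populations and in the listings, and only those who cannot give even a year are affected. Descriptive summaries may include n (SAP 3.4.1), which would hint at the number missing but would not identify why.

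4. **The midpoint is a choice, not a fact.** This also stands, as Step 5 shows.

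A reader might infer more than the text supports. One tempting reading is that age at onset is wrong in both groups; in the older group it is missing, not wrong. Another is that omitting long-standing cases makes the summary too old. The category records time since onset, not age at onset: a 60-year-old with onset at 50 also belongs to the older group. At a given current age the omission does remove earlier onsets, but the overall direction depends on an age mix that the documents do not give.

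**Conclusion.** The point holds as a small correction. For wholly unknown onsets recorded as under 5 years ago, the stated rule gives a value that contradicts the recorded answer and biases age at onset low by up to 5 years per subject. The direction follows from the text alone; the average size (−0.5 to −4.5 years across the cases above, −2.5 if uniform) rests on assumed values of T. The effect on the overall mean depends on how many subjects are affected, which the documents do not say.

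For undatable older onsets, the defect is an omission from one statistic with no requirement to report how many are omitted. Any bias from it has unknown sign and may be nil. The mismatch between 3.1.10 and 3.5.3 at exactly 5 years is a separate wording error.

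The consequence is limited to a descriptive baseline characteristic. The safety objective, the CR-PCSS responder summaries and the sample size are untouched.

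**What to change.** 1. In SAP 3.5.3, define the two categories as in 3.1.10, so that exactly 5 years falls in the older group.
2. Impute the under-5 group inside its interval, for example at consent minus 2.5 years, stated as an assumption; or do not impute it and leave age at onset missing.
3. In the SAP 3.4.4 table, add a row with the number of subjects whose onset was 5 or more years ago with date unknown. If the under-5 group is not imputed, give its count as well.
4. Summarize EFP duration as under 5 versus 5 or more years for all subjects. The answer is already collected for wholly unknown dates, so they need no imputation; partly known dates are classified under the existing 1st/January rule.

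The cost is two SAP sentences and one or two table rows, with no new data collection. The drawback is that the midpoint is less accurate than the current rule if true onsets cluster at 4–5 years. The duration row avoids that dependence for wholly unknown dates.

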3.5.4. Relative Study Day/Treatment Session Study Day

Relative study day will be computed for each visit and for each AE. For visits or events occurring on or after the Day 1 visit, relative study day will be date of visit (event) – date of first injection + 1. For visits or events that occur prior to the Day 1 visit, the relative study day will be the date of visit (event) – date of first injection.

3.5.5. Conventions and Algorithms

3.5.5.1. Summary Tables/Subject Listings Conventions

Summary tables, subject listings, graphs and any supportive SAS output will include a “footer” of explanatory notes that will indicate, when applicable:

- date of data extraction
- date and time of output generation
- SAS program name that generated the output

Null summary tables will be presented with a note stating that “No Subjects Met Criteria.”

All summary tables involving percentages will round the percentages off to 1 decimal place. All summary tables involving descriptive statistics of continuous variables will round the mean and median to 1 decimal place more than the variable’s standard form and round the standard deviation to 2 decimal places more than the variable’s standard form. The standard form of a percent change variable is 0 decimal places.

When summarizing AEs, potentially clinically important laboratory, and potentially clinically important vital signs, subjects with multiple occurrences of an event will be counted only once in the summary. When AEs are summarized by severity, if the subject has multiple occurrences of the same AE, the most severe will be used for the summary.

Individual subject listings will be provided as support for summary tables and serve as a data source substitute when a summary table is deemed either inappropriate or unnecessary. All subject listings will be sorted by subject number. When applicable, the subject listings will include the visit date, and days relative to the start of first treatment and start of treatment session.

3.6. INTERIM ANALYSES

No interim analysis is planned for this study.

3.7. SAMPLE SIZE CALCULATION

To have a sufficient safety database of subjects establishing safety following exposure to EN3835, up to 150 subjects will be enrolled and monitored for 6 months in accordance with International Conference on Harmonisation (ICH) guidance.

3.8. TABLES, LISTINGS, AND GRAPHS SHELLS

The layouts of the summary tables, subject listings, and graphs are presented in SAP Module 2. These layouts incorporate all the appropriate table/listing/graph titles, numbers, and footnotes.
